7.5 Pharmacokinetic Analyses

PK samples will be collected at baseline and at multiple time points after the complete dose was administered from up to 100 subjects enrolled at a subset of sites in Canada and the US.

Actual sampling time-points will be recorded and used for PK calculations. If data permit, the following PK parameters for NA-1 will be calculated at the end of the study by standard noncompartmental methods for all subjects with PK samples:

- AUC_{0-t}: Area under the concentration-time curve from time zero to time of last measurable concentration

- AUC_{0–inf}: Area under the concentration-time curve from time zero to infinity
- C_{max}: Maximum plasma concentration observed after dosing
- T_{max}: Time to occurrence of C_{max}
- t_{1/2}: Terminal elimination half-life

Samples with no detectable NA-1 will be excluded from analysis (placebo).

Descriptive statistics will be calculated for NA-1 plasma concentrations and for all PK parameters (AUC_{0–t}, AUC_{0–∞}, C_{max}, T_{max}, t_{1/2}).

A further analysis of the effect of administration of thrombolytic therapy (alteplase) on the pharmacokinetics of NA-1 will also be performed.

Depending on the ability to obtain an adequate number of PK samples, the SAP may be amended (providing that no unblinding of treatment allocation has taken place) to optimize the PK analysis, including the possibility of popPK analyses in the event that only sporadic samples are obtained from subjects due to operational limitations.

Table 2. Summary of Inferential Efficacy Analyses

Endpoint Type	Endpoint	Scale	Population	Statistical Model
Primary	Day-90 mRS	Binary (≤ 2 vs. > 2)	ITT	logit(binary mRS) modeled as a function of treatment, baseline ASPECTS, occlusion location, age, sex, baseline NIHSS, alteplase*thromb_app, study site
	Day-90 mRS	Binary (≤ 2 vs. > 2)	PP	logit(binary mRS) modeled as a function of treatment, baseline ASPECTS, occlusion location, age, sex, baseline NIHSS, alteplase*thromb_app, study site
	Day-90 mRS	Binary (≤ 2 vs. > 2)	ITT, re-randomization	logit(binary mRS) modeled as a function of treatment, baseline ASPECTS, occlusion location, age, sex, baseline NIHSS, alteplase*thromb_app, study site; run model on 5,000 re-randomized ITT populations
	Day-90 mRS	Binary (≤ 2 vs. > 2)	PP	logit(binary mRS) modeled as a function of treatment, baseline ASPECTS, occlusion location, age, sex, baseline NIHSS, alteplase*(actual first endovascular approach), study site
Secondary	Day-90 mRS	Ordinal (0-4,5+6)	ITT	mRS cumulative logits modeled as a function of treatment, baseline ASPECTS, occlusion location, age, sex, baseline NIHSS, alteplase*thromb_app, study site
	Day-90 NIHSS	Binary (≤ 2 vs. > 2)	ITT	logit(binary NIHSS) modeled as a function of treatment, baseline ASPECTS, occlusion location, age, sex, baseline NIHSS, alteplase*thromb_app, study site
	Day-90 Barthel	Binary (< 95 vs. ≥ 95)	ITT	logit(binary Barthel Index) modeled as a function of treatment, baseline ASPECTS, occlusion location, age, sex, baseline NIHSS, alteplase*thromb_app, study site
	Day-90 Mortality	Binary day-90 death status	ITT	logit(binary death status) modeled as a function of treatment, baseline ASPECT, occlusion location, age, sex, baseline NIHSS, alteplase*thromb_app, study site
	Day-90 mRS	mRS Binary (≤ 1 vs. > 1)	ITT	logit(binary mRS) modeled as a function of treatment, baseline ASPECTS, occlusion location, age, sex, baseline NIHSS, alteplase*thromb_app, study site
Tertiary	EQ-VAS	0-100	ITT	EQ-VAS modeled as functions of treatment, baseline ASPECTS, occlusion location, age, sex, baseline NIHSS, alteplase*thromb_app, study site
	Stroke volume	continuous	ITT	Stroke volume (or cubic root transformation of stroke volume) modeled as a function of treatment, baseline ASPECTS, occlusion location, age, sex, baseline NIHSS, alteplase*thromb_app, study site
	BNT15	0-15	ITT	BNT15 Score modeled as a function of treatment, baseline ASPECTS, occlusion location, age, sex, baseline NIHSS, alteplase*thromb_app, study site
	SNAP	0-100	ITT	Total SNAP Score modeled as a function of treatment, baseline ASPECTS, occlusion location, age, sex, baseline NIHSS, alteplase*thromb_app, study site
	MoCA	Binary (< 26 vs. ≥ 26)	ITT	logit(binary MoCA) modeled as a function of treatment, baseline ASPECTS, occlusion location, age, sex, baseline NIHSS, alteplase*thromb_app, study site
	Day-30 mRS	Binary (≤ 2 vs. > 2)	ITT	logit(binary mRS) modeled as a function of treatment, baseline ASPECTS, occlusion location, age, sex, baseline NIHSS, alteplase*thromb_app, study site
Exploratory	Day-90 mRS	Binary (≤ 2 vs. > 2)	ITT	Separate logistic regression models in which the logit(binary mRS) is modeled as a function of treatment only, by each of the subgroups to be considered in the Subgroup forest plots
	Day-90 mRS	Binary (≤ 2 vs. > 2)	ITT	logit(binary mRS) modeled as a function of treatment, baseline ASPECTS, occlusion location, age, sex, baseline NIHSS, alteplase*thromb_app, study site, period, and treatment by period interaction

Statistical Analysis Plan

Endpoint Type	Endpoint	Scale	Population	Statistical Model
	All secondary endpoints	As listed above	ITT	Modeled as described above as a function of treatment, baseline ASPECTS, occlusion location, age, sex, baseline NIHSS, alteplase*thromb_app, study site, period, and treatment by period interaction
	Day-90 mRS	Binary (≤ 2 vs. > 2)	ITT	logit(binary mRS) modeled as a function of treatment, baseline ASPECTS, occlusion location, age, sex, baseline NIHSS, alteplase*thromb_app, study site, and time between tPA administration and infusion start

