6.2 Randomization and Blinding

Treatment will be assigned using 1:1 randomization (placebo:NA-1) centrally, using a web-based algorithm with treatment assignment allocated by web-based real-time interaction with the site. Randomization will be fully concealed by having both dynamic real-time allocation based upon random number generation and visually identical appearing NA-1 and placebo vials. All vials will have a unique vial number.

In order to minimize differences between the two treatment arms of the trial other than the investigational treatment, the protocol will restrict the use of multiple non-randomized intra-arterial therapies and stratify randomization by (a) use of intravenous thrombolysis with alteplase (yes/no) and (b) the declared first thrombectomy approach. The intended first thrombectomy approach will be restricted to the use of either a stent retriever or clot aspiration device. The intent to use any other endovascular device type or intra-arterial medications as the initial thrombectomy approach constitutes an exclusion criterion. Additionally, if intravenous thrombolysis is planned for the subject, the intent to use any intravenous thrombolytic other than alteplase is an exclusion criterion.

Thus, randomization will be stratified by declared first thrombectomy approach which will be dichotomized as stent retriever vs aspiration device, and by intravenous alteplase use (yes/no). Within each stratum, a randomized minimization procedure will occur on 6 baseline prognostic variables. Subject data required for randomization are age, sex, baseline NIHSS scores, baseline ASPECTs score, occlusion location and site.

The purpose of stratification is to provide increased certainty that equal or near-equal proportion of patients in each stratum will receive NA-1 or placebo.

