8.8 Pharmacokinetics Substudy

In order to assess Pharmacokinetics in the patient population, PK samples will be collected at baseline and at multiple time points after the complete dose was administered from up to 100 subjects enrolled at a subset of sites in Canada and the US.

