8.8.1 PK Sample Collection

A total of six 2 mL blood samples for PK assessment will be drawn during the Baseline Visit. Time (T) =0 being the initiation of dosing of study drug or placebo. Samples will be drawn at the following timepoints:

- Sample 1: post randomization & prior to start of study drug administration (Time=0 min)
- Sample 2: 10 minutes from start of study drug administration (Time = 10 min)
- Sample 3: 20 minutes from start of study drug administration (Time = 20 min)
- Sample 4: 30 minutes from start of study drug administration (Time = 30 min)
- Sample 5: 60 minutes from start of study drug administration (Time = 60 min)
- Sample 6: 120 minutes from start of study drug administration (Time = 120 min)

At each timepoint a 2 mL sample of blood will be collected in tubes provided by the Sponsor. Sample collection method should be the least invasive to the subject and may be combined with routine blood sampling.

The samples will be handled per guidelines/instructions provided by the sponsor. These tubes are labeled with adhesive labels that identify the study code, site number, the subject's number, and the sample date and time. A minimum of 1.0 mL of plasma will be transferred into each cryovial.

The date and time for each step (blood draw, storage, centrifugation, aliquoting, and freezing) and the number of aliquots obtained must be documented in the source document.

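### The PK rule identifies placebo by an undetectable assay result, so as written it also drops undetectable samples from NA-1 subjects and can weaken the alteplase comparison at late times

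*SAP*

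**What the plan says.** The substudy takes blood "from up to 100 subjects enrolled at a subset of sites in Canada and the US" (Protocol 8.8). Allocation in the trial is equal: "Treatment will be assigned using 1:1 randomization (placebo:NA-1") (Protocol 6.2). Six samples are planned per subject. The first is described as "Sample 1: post randomization & prior to start of study drug administration (Time=0 min") and the last as "Sample 6: 120 minutes from start of study drug administration (Time = 120 min"); the others are at 10, 20, 30 and 60 minutes (Protocol 8.8.1).

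SAP 7.5 says that the PK parameters "will be calculated at the end of the study by standard noncompartmental methods for all subjects with PK samples", if data permit. AUC0-t is defined as "Area under the concentration-time curve from time zero to time of last measurable concentration". Placebo is then dealt with in one sentence, which also stands in Protocol 9.8: "Samples with no detectable NA-1 will be excluded from analysis (placebo"). The next analysis named is: "A further analysis of the effect of administration of thrombolytic therapy (alteplase) on the pharmacokinetics of NA-1 will also be performed".

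Both documents plan descriptive statistics of plasma concentrations, and Protocol 11.6.5 adds plots of mean concentration over time. Neither document gives a detection limit, a half-life for NA-1, a method for the alteplase analysis, or any other rule for undetectable values in treated subjects.

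**The concern.** An undetectable result is not the same as placebo. The T=0 sample is taken before any drug is given, so it should be undetectable in every NA-1 subject. Protocol 8.7.1 states that no significant amount of NA-1 is left in the blood at 24 hours, so treated subjects do become undetectable at some point; whether any do by 120 minutes is not stated. SAP 6.2 lists a missed or incomplete dose and a wrong vial among possible deviations. An NA-1 subject with no measurable drug is thus a case that PK data could reveal and that this rule would discard.

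The proxy is also unnecessary. PK parameters are calculated at the end of the study, and Protocol 6.3 releases the codes after data lock at that time. SAP 2.2 already groups subjects by treatment received for safety.

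At stake is the alteplase analysis. If alteplase lowers NA-1, more samples from alteplase subjects fall below the limit and are dropped, so the comparison is made on samples selected by its own outcome. The outputs most exposed are the late concentration summaries and any summary from which a wholly undetectable subject disappears.

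**Working it through.** The plan states no figure for this analysis, so there is none to reproduce. The detection limit, the half-life and the alteplase effect are all assumptions below.

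**Number of NA-1 subjects.** Up to 100 subjects at 1:1 gives about 100 × 1/2 = 50 on NA-1, then divided by alteplase use.

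**1. One late time point.** Assume log-normal concentrations with log-scale SD s = 0.6, median 1 without alteplase and R = 0.50 with alteplase. Let L be the detection limit as a fraction of the no-alteplase median.

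- a0 = ln(L)/s and a1 = [ln(L) − ln(R)]/s
- share dropped = Φ(a)
- λ(a) = φ(a)/[1 − Φ(a)]
- geometric mean of the detectable samples = median × exp(s·λ(a))
- ratio under the rule = R × exp{s·[λ(a1) − λ(a0)]}

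For L = 0.5: a0 = −1.155, λ(a0) = 0.234; a1 = 0, λ(a1) = 0.798. The ratio is 0.50 × exp{0.6 × (0.798 − 0.234)} = 0.70.

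| L | Dropped, no alteplase | Dropped, alteplase | Ratio under the rule (true 0.50) | Ratio under the rule (true 0.70) |
|---|---|---|---|---|
| 0.3 | 2% | 20% | 0.60 | 0.75 |
| 0.5 | 12% | 50% | 0.70 | 0.81 |
| 0.7 | 28% | 71% | 0.77 | 0.86 |

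The dropped shares are for the true ratio of 0.50. At L = 0.5 the geometric mean without alteplase is also inflated, by exp(0.6 × 0.234) = 1.15.

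**2. Whole profile.** This is a simulated one-compartment model with a 10-minute infusion and the protocol's sampling times. Assumptions: half-life 10 or 20 minutes, limit 1% or 5% of a nominal peak scale, and between-subject log SD 0.4 for exposure and 0.3 for half-life. Ratios are alteplase to no alteplase.

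- *Exposure halved (true 0.50).* Under the rule Cmax is 0.50 and AUC0-t is 0.45 to 0.49. Keeping undetectable samples as zero gives practically the same AUC0-t, because that parameter stops at the last measurable value anyway. The mean concentration ratio is 0.50 to 0.80 at 60 minutes and 0.64 to 0.87 at 120 minutes. The top of the last range rests on very few detectable samples.
- *Half-life halved.* AUC0-t under the rule is 0.48 to 0.50 against a true AUC ratio of 0.49 to 0.53. The 60-minute mean concentration ratio is 0.27 to 0.74 against a true 0.07 to 0.21.
- *Exposure 90% lower.* Cmax under the rule is 0.10 to 0.11, so the fall is plain.
- *30% of alteplase subjects wholly undetectable, the rest unchanged.* The true ratio is 0.70 × 1 + 0.30 × 0 = 0.70. The rule deletes the 30% and compares like with like, so the expected ratio is 1.00; the simulation gives 0.99 to 1.01 for AUC and Cmax. Keeping these subjects as zero gives 0.69 to 0.71.

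**3. Pre-dose sample.** If the T=0 sample is dropped and not reset to zero, the first AUC segment is lost. AUC0-t without alteplase then falls by 14% to 27% over the same assumptions.

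**The case against.** The tag in brackets shows what was meant: to take out placebo data. Read with standard noncompartmental methods and parameters for all subjects with PK samples, the sentence may be loose drafting. That is fair as to intent, but the sentence says samples, and a programmer who followed it would delete valid data. Read per subject, it would still class an NA-1 subject with no measurable drug as placebo.

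A reader might infer that the rule strips out low values generally, or hides any lowering of NA-1 by alteplase. The documents do not support either. Only undetectable samples are excluded. A fall that leaves the 10 to 30 minute samples measurable is visible in Cmax and AUC0-t, and AUC0-t by its definition ignores trailing undetectable samples whatever the rule. Where exposure is halved, AUC0-t errs slightly away from no effect.

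It also stands that the plan names no comparison of a single late concentration by alteplase use, and that no post-dose sample up to 120 minutes is known to be undetectable. The pre-dose loss is certain under a literal reading, but it touches both alteplase groups. Full masking needs subjects with no measurable drug even at the end of the infusion, and nothing in the documents suggests that this is common.

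**Conclusion.** The rule as written is wrong in kind: it uses the measured outcome in place of a treatment code that will be available. Under a literal reading, every NA-1 pre-dose sample is excluded, and so are post-dose undetectable samples and wholly undetectable NA-1 subjects, if there are any.

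Two consequences follow. Late mean concentrations can be biased upward, with their alteplase ratio moved toward 1. An alteplase effect that takes some subjects wholly below the limit can be masked in every parameter. Cmax and AUC0-t are otherwise little affected, provided that the pre-dose value is set to zero.

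The late-time ratio of 0.60 to 0.77 in place of 0.50 rests on an assumed log SD of 0.6 and a limit of 0.3 to 0.7 of the no-alteplase median. The documents cannot confirm or narrow that range. The analysis is a descriptive substudy of up to 100 subjects and does not enter the primary or secondary efficacy tests. This is a free improvement of low severity.

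**What to change.** Replace the sentence in SAP 7.5, and match it in Protocol 9.8, with a rule on these lines:

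- Exclude placebo subjects by actual treatment received, using the treatment code after unblinding. Keep every NA-1 subject with PK samples.
- State the assay's detection limit.
- Set undetectable pre-dose samples to zero.
- Treat undetectable post-dose samples as below the limit: censored in concentration summaries, with AUC0-t still ending at the last measurable value. Substituting half the limit is best avoided, since it adds invented terminal points that can distort t1/2 and AUC0-inf.
- Report the number of undetectable samples by time point and alteplase use, and list any NA-1 subject with no measurable drug.

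The cost is a few sentences. No new samples or assays are needed. SAP 7.5 already allows for amending the PK analysis before unblinding, although it ties this to the number of samples obtained; the change should be made before then.

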8.0 SAFETY ANALYSES

The safety population will consist of all subjects who received any dose of study drug. The main analyses will be frequency of SAEs and 90-day mortality. It is expected that the safety population and the ITT population will be near-identical.

8.1 Adverse Events

Additional analyses will consider the frequency of AEs and discontinuations due to AEs.

AEs will be collected until Day 30 and SAEs will be collected until Day 90 or the final contact. AEs will be summarized by presenting, for each treatment group, the number and percentage of subjects having at least one AE, having an AE in each body system and preferred term, by severity and relatedness to study medication. The frequencies and incidences of AEs occurring in subjects in the drug and placebo control groups will be summarized within treatment group by the Medical Dictionary for Regulatory Activities (MedDRA) System Organ Class (SOC). The frequencies and incidences of discontinuations due to AEs occurring in subjects in the NA-1 and placebo control groups will be summarized within treatment group.

If a given subject had more than one AE mapped to the same preferred term, then that subject will be counted only once within that preferred term.

When reporting TEAEs by maximum severity, if a given subject had more than one AE mapped to the same preferred term, then that AE will be counted once according to the maximal level of severity (Severe, Moderate, Mild).

When reporting TEAEs by relationship to study treatment, if a given subject had more than one AE mapped to the same preferred term, then that AE will be counted once according to the highest level of relatedness (Related, Probably, Possibly, Unrelated).

The following summaries (tables) of AEs and TEAEs will be provided by number (percentage) of subjects for each treatment group:

- All TEAEs by MedDRA preferred term

- All TEAEs by MedDRA SOC and by preferred term
- TEAEs (with a start date 0-30 days) by MedDRA SOC and by preferred term
- Serious TEAEs (with start date 0-90 days) by MedDRA SOC and by preferred term
- All TEAEs resulting in death by MedDRA SOC and by preferred term
- Event rate (%) for Serious TEAEs over the 90-day study period between NA-1 and placebo control subjects will be compared by a logistic regression model similar to that of the primary analysis.
- All TEAEs occurring in at least 5% of subjects in either treatment arm, by MedDRA SOC and by preferred term.
- All TEAEs by maximum severity (Severe, Moderate, Mild) by MedDRA SOC and by preferred term. Missing severity grades will be assumed as 'severe'.
- All TEAEs by relationship to study treatment (Related, Probably, Possibly, Unrelated) by MedDRA SOC and by preferred term. Missing relationships will be assumed as 'related'.
- All TEAEs resulting in discontinuation of treatment, by MedDRA SOC and by preferred term
- TEAEs (onset 0-120 minutes post end of study drug infusion and of special interest as defined in Appendix 1) by MedDRA SOC and by preferred term
- The following listings of AE occurrences will be provided:
 - All AEs by MedDRA SOC and by preferred term
 - All SAEs by MedDRA SOC and by preferred term
 - All AEs leading to death by MedDRA SOC and by preferred term
 - All AEs related to study drug by MedDRA SOC and by preferred term
 - All deaths by treatment group

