4.4 Summary of Known Potential Risks and Benefits

4.4.1 Phase 1 Study

A Phase 1, randomized, fasting, double-blind, placebo-controlled, safety, tolerability, and pharmacokinetic study evaluated single ascending doses of intravenous NA-1 in healthy male and post-menopausal or surgically sterile female human subjects (Biovail Contract Research Study 3301). The primary objectives of this study were to determine the safety and tolerability of single ascending intravenous doses of NA-1. Sixty-two normal, healthy, non-smoking male and post-menopausal or surgically sterile female subjects were dosed in eight cohorts. Subjects received a single dose of NA-1 or placebo on Day 1 of the study period, according to a randomization scheme. NA-1 was given as follows, with the dose increasing per cohort: 0.02, 0.08, 0.20, 0.375, 0.75, 1.50, 2.6 and 3.75 mg/kg of active drug, given as a 10 ± 1 minute intravenous infusion. Subjects were required to return on Days 7, 14 and 28 for interim and end-of-study procedures. There were no SAEs; the majority of noted AEs were mild in severity; no subjects failed to complete the study protocol; and no subjects withdrew from the study. Forty subjects experienced a total of 168 AEs. Thirty-four of the 46 active treated subjects (73.9%) experienced at least one AE, while six of 16 placebo treated subjects (37.5%) experienced at least one AE. Of the 168 AEs, 103 were listed as probably related to the study drug and five AEs were possibly related to the study drug. No severe AEs were reported while 160 of the 168 AEs were mild in severity and eight were moderate in severity. The most commonly reported AEs in subjects receiving any dose of NA-1 were flushing (22% of subjects), dry mouth (20%), feeling hot (20%), dizziness (17%), localized pruritis (15%), decreased blood pressure (BP;11%), generalized rash (9%), generalized erythema (9%), nausea (9%), increased blood glucose (9%), increased alanine aminotransferase (9%), oral hypoaesthesia (9%), paraesthesia (9%), generalized pruritis (7%), urine positive for white blood cells (7%), and localized rash (7%). The incidence of AEs in the 30 subjects receiving NA-1 at dose levels of 0.02, 0.08, 0.20, 0.375, 0.75 and 1.50 mg/kg was the same as that of the 16 placebo treatment subjects. Subjects in the 2.6 and 3.75 mg/kg dose groups experienced more AEs than subjects in the lower dose groups, though none was serious. Overall, NA-1 was well tolerated as a single intravenous dose in the range of 0.02 to 2.6 mg/kg, administered to healthy male and post-menopausal or surgically sterile female subjects.

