8.1.1.2 Dose Administration

Dosing will be carried out by, or under the supervision of, the trial physician who is supervising the care of the subject for the planned or ongoing endovascular reperfusion procedure.

A syringe for each individual subject dosing will be prepared by calculating the volume to draw from the vial as follows: for subjects weighing less than 105 kg: $(2.6 \text{ mg/kg} \times \text{subject weight in kg}) / (20 \text{ mg/ml})$. This will determine the number of mL to pull up into the syringe. For subject weighing 105-120 kg the full volume of one vial (13.5mL, equivalent to 270 mg of NA-1) will be used.

The syringe containing study drug will be injected into the intravenous port of a 50 or 100 mL drip bag of 0.9% normal saline that has been labeled with the randomization number and subject's age. The bag will be mixed by squeezing and inverting the bag several times. After dilution into the drip bag, the drug is stable for up to 5 hours, however it should be infused into the subject as soon as practical with a target randomization to treatment time of 30 minutes or less.

An appropriate sized syringe must be used, such that this volume is between 20% and 100% of the delineated markers on the syringe. Once a volume of drug has been drawn into the syringe, the vial will be marked as "used" and placed into a separate vial storage area.

Dosing will be performed by administering the contents of the bag of study drug to the subject through an intravenous catheter inserted into a vein in the upper or lower extremity and using a standard infusion pump. Dosing will be carried out evenly over the course of 10 ± 1 minutes while the intravenous bag contents are administered to the subject. The entire volume (treatment dose) of the intravenous mini-bag must be administered.

After the dose administration, a minimum of 10 mL of saline will be administered using the infusion pump, to flush any remaining medication left within the intravenous tubing. This method of dose administration is identical to that previously conducted in the Phase 2 ENACT trial¹¹. In the event that a subject is concomitantly receiving alteplase therapy, dose administration of NA-1 will be conducted through a separate intravenous catheter inserted into an extremity not containing the alteplase line. If alteplase therapy has been completed, the same intravenous catheter may be used after it has been flushed with saline.

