10.2 Clinical Management of Adverse Events

10.2.1 Early Study Drug Cessation

The intervention is the intravenous administration of 2.6 mg/kg (up to a maximum of 270 mg) of NA-1 over a 10 ± minute intravenous infusion to subject undergoing endovascular mechanical thrombolysis/thrombectomy. It is expected that dosing will be completed before the endovascular procedure is completed. However, if dosing is ongoing during the endovascular procedure, dosing will not be stopped in the event of an adverse intra-procedural event deemed to be a complication of the endovascular intervention.

If any SAE is observed during dosing, dosing shall be immediately terminated. If any moderate or severe AE is observed, the physician may terminate drug administration at his/her discretion.

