10.2.3 Increases in Histamine

NA-1 has undergone preclinical testing in rats, dogs, rabbits, and non-human primates. When administered in these animals at doses higher than the one proposed in the current clinical trial, NA-1 has produced apparent anaphylactoid events characterized by histamine release in rats and dogs. The observed signs and symptoms were compatible with the physiological effects of histamine; specifically, transient hypotension and hives. This raises the possibility that anaphylactoid reactions to NA-1 could occur in humans. Patient susceptibility to drug-induced anaphylactoid events is highly variable. Therefore, potentially severe anaphylactoid reactions to the study drug may be encountered. Anaphylactoid reactions, including histamine-related reactions such as urticaria, bronchoconstriction, or hypotension, should be monitored. In the event that an anaphylactoid reaction requiring treatment occurs, treatment should follow the same algorithms as would be followed if a spontaneous anaphylactoid reaction occurred in the community.

- Follow emergency medicine ABCs and establish airway first.
- Treat hypotension with crystalloid, colloid and/or vasopressors as needed (see [Section 10.2.2](#)).
- Consider treatment with antihistamine agents (diphenhydramine 50 mg IV, ranitidine 50 mg IV) and corticosteroids if the reaction is severe.
- Consider using subcutaneous or intravenous epinephrine.
- If bronchospasm or laryngospasm are important symptoms, consider treatment with inhaled racemic epinephrine.

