1.7 Definitions

Baseline: A subject's baseline value for a given endpoint or parameter is defined as his/her latest measurement taken prior to study drug administration.

Prior and Concomitant Medications: Prior medications are defined as those taken within three days of treatment initiation. Concomitant medications are defined as those taken during study drug administration or after study drug has been administered through and including the Day 30 visit. All prior and all concomitant medications will be recorded on the electronic case report form (e-CRF).

Randomization: The time of randomization is defined as the time randomization occurred on the central server and this time is considered time zero for the study. All time windows are calculated from the time of randomization.

Treatment-Emergent Adverse Event: A treatment-emergent adverse event (TEAE) is one that first occurs or worsens in severity or frequency after study drug has been administered through to and including the Day 30 visit. SAEs are collected through the last study visit. Those AEs that start at the same time and date as the study drug administration and those that first occur or worsen after the start of study drug administration will be considered TEAEs.

AEs with partial or missing dates will be handled as follows:

- If the start day and/or month of the AE is missing and the AE in question occurs concurrently or subsequent to the study drug administration, the AE will be considered treatment-emergent.
- If the start date is completely missing then the AE will be considered treatment-emergent.

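### The special-interest adverse event table in SAP 8.1 starts its clock at the end of infusion, so acute reactions that begin while the drug is running, and do not stop it, fall outside it

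*SAP*

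**What the plan says.** SAP 8.1 lists the adverse event tables. One is reserved for events of special interest: "TEAEs (onset 0-120 minutes post end of study drug infusion and of special interest as defined in Appendix 1". Appendix 1 gives preferred terms only, in three groups (angioedema, hypotension, and anaphylactic reaction or shock), and sets no onset window of its own.

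SAP 1.7 starts the treatment-emergent clock earlier: events that start at the time of administration count, and "those that first occur or worsen after the start of study drug administration will be considered TEAEs". Protocol 8.1.1.2 gives the infusion length: "Dosing will be carried out evenly over the course of 10 ± 1 minutes".

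SAP 8.1 also plans a table of "All TEAEs resulting in discontinuation of treatment, by MedDRA SOC and by preferred term". SAP 8.2 adds an ANCOVA of maximum blood pressure deviation from baseline to 24 hours, and vital signs include a reading at completion of infusion.

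Protocol 10.2.1 sets out when dosing ends early. Apart from complications of the endovascular procedure, dosing ends for any SAE. For other events, "If any moderate or severe AE is observed, the physician may terminate drug administration at his/her discretion". It states no stop for a mild, non-serious event.

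**The concern.** The two SAP sections use different starting points. Under SAP 1.7 an event in the fifth minute of the infusion is treatment-emergent. Under SAP 8.1 the special-interest table does not open until the infusion has ended, so a programmer following the text would exclude that event.

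Protocol 10.2.3 describes histamine-type events in animals at higher doses and says "This raises the possibility that anaphylactoid reactions to NA-1 could occur in humans". The special-interest table is the only one in SAP 8.1 built around reactions of that kind. Its short window also gives it specificity: Appendix 1 includes broad terms, such as acute kidney injury, respiratory failure and peripheral oedema, that can arise for many other reasons over 30 days. A table with this purpose should not leave out the minutes during which the drug is being given. At stake is an incomplete count in a descriptive safety table, not the loss of events from the database.

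**Working it through.** **Inputs**

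- Special-interest window: 0 to 120 minutes from the end of infusion (SAP 8.1).
- Treatment-emergent: onset at or after the start of administration (SAP 1.7).
- Planned infusion length: D = 10 minutes, range 9 to 11 (Protocol 8.1.1.2).

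**Interval check.** Let t be onset in minutes from the start of infusion.

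- Treatment-emergent: t ≥ 0.
- In the table as written: 0 ≤ t − D ≤ 120, that is D ≤ t ≤ D + 120.
- Treatment-emergent but too early for the table: 0 ≤ t < D, which is the whole infusion up to its recorded stop time.

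With D = 10:

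| Onset t (min) | Treatment-emergent | In table as written | In table if the window runs from start to end + 120 |
|---|---|---|---|
| 0 | yes | no | yes |
| 2 | yes | no | yes |
| 5 | yes | no | yes |
| 9.9 | yes | no | yes |
| 10 | yes | yes | yes |
| 60 | yes | yes | yes |
| 130 | yes | yes | yes |
| 131 | yes | no | no |

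The revised window spans 10 + 120 = 130 minutes (129 to 131 for infusions of 9 to 11 minutes). It keeps every onset the current window holds and adds those during infusion.

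**Does another SAP 8.1 table separate these events?** The other tables cover:

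- all treatment-emergent events (by preferred term, and by SOC and preferred term);
- start date 0–30 days;
- serious events 0–90 days, and the serious-event rate by logistic regression;
- events resulting in death;
- events in at least 5% of either arm;
- maximum severity;
- relationship to treatment;
- discontinuation of treatment.

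None filters on Appendix 1 terms or isolates the infusion period. The discontinuation table picks out infusion-time reactions only when they stopped dosing. The blood pressure ANCOVA in SAP 8.2 does not classify adverse events by onset and does not address flushing, rash, bronchospasm or angioedema.

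**Can a reaction begin during infusion without stopping it?** Yes. Under Protocol 10.2.1, stopping is discretionary for moderate or severe non-serious events, and no stop is stated for mild ones.

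**Are such reactions plausible?** Protocol 4.4.1 reports Phase 1 in healthy subjects given NA-1 0.02–3.75 mg/kg or placebo: "No severe AEs were reported while 160 of the 168 AEs were mild in severity and eight were moderate in severity". That is 160/168 = 95.2% mild and 8/168 = 4.8% moderate. The most common events in NA-1 subjects included several with counterparts in Appendix 1: flushing (22%), decreased blood pressure (11%), generalized rash (9%), generalized erythema (9%) and generalized pruritus (7%). Phase 1 onset times are not reported, so these figures show plausibility only. They do not estimate how many events would be missed.

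**The case against.** The strongest reply is that no event is lost. Every such reaction appears by arm and preferred term in the all-event, 0–30 day, severity and relationship tables, and in the listings. The relationship table and the listing of related events are especially useful. Protocol Table 10-1 rests the probable and possible categories on a reasonable time sequence to dosing, and SAP 8.1 treats a missing relationship as related, so most mid-infusion reactions would probably be set apart from unrelated events. Serious reactions are well covered: an SAE during dosing ends dosing, and it enters the discontinuation table, the serious-event table and the serious-event regression. What remains is non-serious events that did not stop dosing.

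This is correct and limits the consequence. It does not close the gap. The relationship table depends on investigator judgement, mixes in later related events, and splits by neither onset nor Appendix 1 term.

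A second reply is that the Phase 1 figures give a one-sided picture. In the Phase 2 trial (Protocol 4.4.2), which used 2.6 mg/kg, possibly or probably related events were (11 + 2)/336 = 3.9% of NA-1 events and 21/388 = 5.4% of placebo events, and no SAE was related. That balance is fair. The same trial reported hypotension in 10% of NA-1 and 6% of placebo subjects. Neither study gives onset times, so neither settles how many events the window would miss.

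A third reply is that Protocol 10.4 asks only for start and stop dates of adverse events, so clock times may not exist. However, SAP 1.7 compares event time and date with dosing, and the existing 120-minute window cannot be applied without clock times. The change needs nothing that the current table does not already need.

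**Conclusion.** The concern holds and is minor. As worded, the special-interest table leaves out Appendix 1 reactions with onset during the 10 ± 1 minute infusion, unless onset is recorded at the stop time. The main gap is reactions that do not stop dosing, because those that do can be read from the discontinuation table.

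The number of events affected, and the size and direction of any effect on the comparison between arms, cannot be determined from the documents. The table is descriptive. The leading safety outcomes (SAEs and 90-day mortality) are unaffected, and no endpoint or inference changes.

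The conclusion rests on a literal reading of the SAP 8.1 window. If the infusion period was meant to be included, the wording still needs correcting. The statement that no other table separates these events covers SAP 8.1 only: the list of planned outputs that SAP 8.5 places in Appendix A was not in the text available for review.

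**What to change.** In SAP 8.1, redefine the window of the special-interest table as onset from the start of study drug infusion to 120 minutes after the end of infusion. This matches the treatment-emergent definition in SAP 1.7 and drops nothing the table now captures. Make the change before unblinding.

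The cost is one line of SAP wording and the matching table code. Protocol 6.5 already requires infusion start and stop times to be recorded, so no new data collection is needed.
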